11.2.6. Number of decimals displayed

The following decimal description from the decision rules will be used for the demography, immunogenicity and safety/reactogenicity.

Display Table	Parameters	Number of decimal digits
All summaries	% of count, including LL & UL of CI	1
All summaries	% of difference, including LL & UL of CI	2
Demographic characteristics	Mean, median age, SD (age)	1
Reactogenicity	Mean, Min, Q1, Median, Q3, Max for duration	1
Immunogenicity	Ratio of GMT/GMC	2

12. ANNEX 2: SUMMARY ON ELIMINATION CODES

Refer to section [5.2](#)

13. ANNEX 3 CALCULATION OF INDIVIDUAL AND OVERALL DESIRABILITY INDEX

The section below provide the details on how to calculate individual desirability index and overall desirability index score based on Annex E in the Protocol.

Reactogenicity

A logistic regression model will be fitted on each reactogenicity endpoint (any Grade 2/3 general AE and any related SAE, Grade 2/3 fever) reported during the 7-day follow-up period after vaccination, including all RSV formulations.

- The vaccine group as the fixed effect
- The age groups (18-32 years and 33-45 years) as the categorical covariant if deemed necessary.

The estimation of indication rate will be tabulated by treatment group. The SAS codes can be used as reference:

[figure not shown]
```
proc logistic data=React;
  class Treatment AgeGroup / param=glm;
  model response (event='AE')= Treatment| AgeGroup;
  lsmeans Treatment / ILINK e diff oddsratio adjust=bon cl;
run;
```

For any Grade 2/3 general AEs and any related SAEs, the incidence rate estimate (IR) will be transformed in a [0,1] desirability index using the following function:

$$DR1 = \begin{cases} \frac{1}{1 + \exp(-50 * (0.25 - IR))}, & \text{if } IR \leq 0.25 \\ \frac{1}{1 + \exp(-25 * (0.25 - IR))}, & \text{if } IR \geq 0.25 \end{cases}$$

where IR is the incidence rate estimated by the model. This function will allocate a desirability value of 1, 0.5 and 0 to incidence rate equal to 0.1, 0.25 and 0.5 respectively (see Figure 2). But the calculation equally weights Grade 2/3 general AEs and any related SAEs.

Figure 2 Desirability function for the incidence rate of Grade 2/3 general AEs and related SAEs - for each investigational RSV vaccine formulation

[figure not shown]

For Grade 2/3 fever, the incidence rate estimate (IR) will be transformed in a [0,1] desirability index using the following function:

$$DR2 = \frac{1}{1 + \exp(-120 * (0.05 - IR))}$$

where IR is the incidence rate estimated by the model. As illustrated in Figure 3, the function will allocate desirability values of 1, 0.5 and 0 to incidence rate equal to 0, 0.05 and 0.1 respectively.

Figure 3 Desirability function for the incidence rate of Grade 2/3 fever - for each investigational RSV vaccine formulation

Finally, the reactogenicity index will be computed by taking the geometric mean of the 2 indexes:

$$DR = \sqrt{DR1 * DR2}$$

Immunogenicity

The ANCOVA model will be fitted on the log-transformed titre for each immune response of neutralising anti-RSV-A and PCA separately including

- The vaccine group as the fixed effect
- The pre-vaccination titre/concentration and age groups (18-32 years and 33-45 years) as the covariates if deemed necessary

The mean estimations of GMTs/GMCs for each treatment group at Day 30 and its 95% CI will be provided for immunogenicity desirability calculation. The estimated GMT and LL will be tabulated by treatment group.

As formulations inducing a high immune response will be considered suitable, the lower limit (LL) of the estimated GMT/C adjusted for pre-vaccination titres will be the statistical criterion considered for decision making.

[figure not shown]
Neutralising anti-RSV-A titres

The LL of the GMT estimate will be transformed into a [0, 1] desirability index using the function:

$$DI1 = \frac{1}{1 + \exp(1.5 * (9.5 - LL))}$$

where LL is the lower limit of the 95% confidence interval of the GMT adjusted for pre-vaccination titres in log base 2. The function was chosen to have a desirability of 0 at LL value ≤ 6 log2 (=128), and a desirability of 1 at LL value ≥ 13 log2. This function is illustrated in [Figure 4](#).

Figure 4 Desirability function for neutralising anti-RSV-A GMTs - for each investigational RSV vaccine formulation

[figure not shown]
PCA concentrations

The LL of the GMC adjusted for pre-vaccination titres estimate will be transformed using the following function:

$$DI2 = \begin{cases} \frac{1}{1 + \exp(0.05 * (150 - LL))}, & \text{if } LL \leq 150 \\ \frac{1}{1 + \exp(0.025 * (150 - LL))}, & \text{if } LL \geq 150 \end{cases}$$

As illustrated in [Figure 5](#), a PCA response of 25, 150 and 400 µg/mL will have a desirability value of 0, 0.5 and 1 respectively.

Figure 5 Desirability function for PCA concentrations - for each investigational RSV vaccine formulation

Finally, the immunogenicity index will be computed by taking the geometric mean of the 2 indexes:

$$DI = \sqrt{DI1 * DI2}$$

Overall desirability index

The overall desirability index for each formulation will be obtained by computing the following weighted geometric mean: $D = DR^{0.4} * DI^{0.6}$.

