6.4.2. Derived endpoints

The following endpoints will be computed and taken into account in the desirability analysis:

1. Incidence rate of any Grade 2 and any Grade 3 general AE (solicited and unsolicited) and any vaccine-related SAE during the 7-day follow-up period after vaccination for each investigational RSV vaccine formulation.
2. Incidence rate of Grade 2 and Grade 3 fever during the 7-day follow-up period after vaccination for each investigational RSV vaccine formulation.

3. Geometric mean of neutralising antibody titres against RSV-A at Day 30 adjusted for pre-vaccination titres.
4. Geometric mean of PCA concentrations at Day 30 adjusted for pre-vaccination titres.

Each individual desirability index will be calculated based on data and tabulated by the treatment group and endpoints above. The details on how to calculate individual desirability index in terms of reactogenicity and immunogenicity and overall desirability index are elaborated in Annex 2.

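### The reference SAS code for the reactogenicity index fits an age interaction that the text does not specify and back-transforms averaged logits, so its incidence rate can depart from the formulation's rate and falls to about 0 when one age stratum has no fever

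*SAP*

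**What the plan says.** The primary objective is to rank the formulations, and section 6.4.1 ranks them on the overall desirability index. Section 6.4.2 lists the reactogenicity inputs as incidence rates per formulation, for example "Incidence rate of Grade 2 and Grade 3 fever during the 7-day follow-up period after vaccination for each investigational RSV vaccine formulation".

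Annex 3 (section 13) says how these are obtained: "A logistic regression model will be fitted on each reactogenicity endpoint", for the RSV formulations, with vaccine group as fixed effect and "The age groups (18-32 years and 33-45 years) as the categorical covariant if deemed necessary". No interaction is named.

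The code follows, introduced by "The SAS codes can be used as reference". Its two key statements are "model response (event='AE')= Treatment| AgeGroup" and "lsmeans Treatment / ILINK e diff oddsratio adjust=bon cl". The result goes straight into the index: "where IR is the incidence rate estimated by the model". For fever, the function is meant to give "desirability values of 1, 0.5 and 0 to incidence rate equal to 0, 0.05 and 0.1 respectively".

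Annex 3 has no rule for an age stratum without events. Amendments 2 and 3 print the same code.

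**The concern.** Text and code describe different models. In SAS the bar operator expands to both main effects plus their interaction, so the model is saturated in formulation by age.

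`LSMEANS Treatment / ILINK` then averages the two age-specific logits with equal weight and back-transforms the average. That quantity equals the formulation's incidence rate only in special cases, such as equal rates in both strata. DR1 and DR2 are calibrated on incidence rates and are steep, so small departures matter.

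The fever component is the most exposed. Grade 2/3 fever may be rare, and a stratum without events has a maximum-likelihood logit of minus infinity. That pulls the formulation's estimated rate to 0. A formulation could then be ranked on a fever desirability that its data do not support.

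**Working it through.** **Inputs.** About 100 subjects per group (SAP Table 1). Two age strata, 18-32 and 33-45 years (section 2). The SAP gives no age split, so 50 per stratum is an assumption.

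From Annex 3:
- DR2 = 1/(1 + exp(-120 × (0.05 - IR)))
- DR1 has slope 50 up to IR 0.25 and slope 25 above it
- DR = √(DR1 × DR2) and D = DR^0.4 × DI^0.6, so DR2 enters D with exponent 0.2

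**The plan's own figures.** DR2 at IR 0, 0.05 and 0.1 is 0.9975, 0.5000 and 0.0025. DR1 at 0.1, 0.25 and 0.5 is 0.9994, 0.5000 and 0.0019. Both match the stated anchors after rounding.

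**What the code returns.** In the saturated model each stratum logit is the observed one, so IR = ilogit[(logit p1 + logit p2)/2]. For an empty stratum the value depends on where iteration stops. A Fisher-scoring fit stopped near logit -19.

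| Fevers (50 + 50) | Observed rate | IR from code | DR2 from code | DR2 at observed rate | Factor on D |
|---|---|---|---|---|---|
| 0 + 5 | 5% | 0.00003 | 0.9975 | 0.500 | 1.15 |
| 0 + 8 | 8% | 0.00004 | 0.9975 | 0.027 | 2.06 |
| 1 + 7 | 8% | 0.0545 | 0.368 | 0.027 | 1.69 |
| 2 + 6 | 8% | 0.0701 | 0.082 | 0.027 | 1.25 |
| 4 + 4 | 8% | 0.0800 | 0.027 | 0.027 | 1.00 |

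The last column is (DR2 from code / DR2 at observed rate)^0.2. For 0 + 5 it is (0.9975/0.5)^0.2 = 1.15. Early stopping does not rescue the result: for 0 + 5 and 0 + 8, DR2 is at least 0.98 after 4 iterations and at least 0.996 after 8.

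The order can reverse. A formulation with 0 + 12 fevers (12%) gets DR2 0.9975, and one with 2 + 3 (5%) gets 0.529.

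**DR1.** Equal strata at 15% and 35% have a marginal rate of 25% and DR1 0.50. The logits are -1.735 and -0.619, their mean is -1.177, and ilogit gives 23.6%. DR1 is then 0.67.

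**Direction.** With equal strata and rates under 50%, the code's IR lies below the marginal rate. With unequal strata it can lie above: 70 subjects at 15% and 30 at 35% have a marginal rate of 0.7 × 15% + 0.3 × 35% = 21.0%, but the code still returns 23.6%.

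**Dropping the interaction alone.** With 0 + 8 fevers in one formulation and 4 + 4 and 2 + 3 in the others, main effects with ILINK give IR 0.073 and DR2 0.060. Averaging predicted probabilities over the age strata gives 0.080 and 0.027, as observed.

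**Effect on ranking.** Simulation of 200,000 trials with equal immunogenicity and a Grade 2/3 AE rate of 20% in each group, comparing the code's ranking with the ranking on observed rates:
- Fever 2/3/5%: the top formulation differs in about 10% of trials and some rank in about 16%. Where the top differs, the median loss in observed-rate D is 0.011. The loss exceeds 0.05 in about 1.6% of all trials.
- Fever 3/5/8% or 5/5/5%: the loss exceeds 0.05 in about 3% and 4% of trials.

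**The case against.** The strongest reply is that nothing here is mandatory. The code is offered as a reference and age enters only if judged necessary. With age omitted, the model contains group alone and IR equals the observed proportion. This stands: the failure needs age to be included and the code to be followed. It does not remove the contradiction, because this is the only code given and it does not fit the model described above it.

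Several stronger readings are tempting, and the documents do not support them:

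- **That fever would be hidden.** Section 6.3.1.1 requires fever by group in half-degree steps, Templates 20 and 21 show it, and Template 57 prints the fever rate beside DR2. A value near 0 would visibly conflict with the tabulated rate.
- **That the index decides the dose.** Section 6.4 makes it a descriptive tool beside the totality of evidence.
- **That fever carries half the ranking.** Reactogenicity as a whole has weight 0.4, and DR2 has exponent 0.2.
- **That the code always understates the rate.** This fails for unequal strata, as shown above.
- **That harm is as frequent as empty strata.** Exactly one of a formulation's two strata is empty with probability 46%, 34% and 14% at true fever rates of 2%, 3% and 5%. Many of these are cases such as 0 + 1 or 0 + 2, where DR2 is already 0.99 or 0.97. A split of 0 + 5 or worse has probability of only about 0.2%, 0.7% and 1.6% per formulation.

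**Conclusion.** The point holds in conditional form and should be fixed. Annex 3's text and code disagree. If age is included and the code is followed, the IR that feeds DR1 and DR2 is not the formulation's incidence rate. It departs from that rate when the age strata differ, and it tends to 0 when one stratum has no fever.

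A single formulation's D can be inflated about 1.15-fold (0 + 5 fevers) or 2.06-fold (0 + 8). Over repeated trials the top rank changes in about 10%, but mostly between formulations that are close on observed rates. Material losses occur in about 1.6% to 4% of trials.

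These sizes rest on 50 subjects per stratum, the assumed AE and fever rates, and equal immunogenicity. Real differences in immunogenicity, which has weight 0.6, would dilute the rank changes. The pull to 0 from an empty stratum does not depend on the age split.

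**What to change.** In Annex 3, delete the bar operator so that code and text agree, and define IR as the observed proportion per formulation. This is the simplest choice and matches section 6.4.2.

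If age adjustment is kept:
- fit main effects only (`Treatment AgeGroup`);
- compute IR by averaging each formulation's predicted probabilities over the pooled age distribution, instead of inverse-linking a least-squares mean;
- use Firth penalisation when the fit separates, for example when a formulation or an age group has no events.

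The cost is a few lines of SAP text and code and a rerun of the index. No new data are needed.

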14. ANNEX 4: STUDY SPECIFIC MOCK TFL

The following draft study specific mock TFLs will be used. The data display, title and footnote are for illustration purpose and will be adapted to the study specificity as indicated in the TFL TOC.

Note that there may be few changes between the study specific SAP mock TFL and the final TFLs. These editorial/minor changes will not lead to a SAP amendment.

Template #	Table Title	Macro
Template 1	Number of subjects enrolled into the study as well as the number of subject excluded from PPS analysis with reasons for exclusion	%ELIMLIST
Template 2	Number of subjects vaccinated, completed and withdrawn with reason for withdrawal (Exposed set)	%DROP_SUM (OTH=1)
Template 3	Number of subjects vaccinated, completed and withdrawn with reason for withdrawal (Exposed set)	%DROP_SUM (OTH=0)
Template 4	Number of subjects at each visit and list of withdrawn subjects (Exposed set)	%DROPOUT
Template 5	Summary of demographic characteristics (Exposed set)	%DEMOGRA
Template 6	Summary of demographic characteristics by age category (Exposed set)	%DEMOGRA
Template 7	Number of subjects by center (Exposed set)	%CENTER
Template 8	Number of subjects by center for each age category (Exposed set)	%CENTER
Template 9	Number of subjects by country and center (Exposed set)	%CENTER
Template 10	Deviations from specifications for age and intervals between study visits (Exposed set)	%INT_VAL
Template 11	Summary of vital signs characteristics (Exposed set)	%VITAL_SIGNS
Template 12	Study Population (Exposed set)	%CTR_DEMOG
Template 13	Number of enrolled subjects by country	%FREQ_DIS
Template 14	Number of enrolled subjects by age category	%FREQ_DIS
Template 15	Minimum and maximum activity dates (Exposed set)	%DATE
Template 16	Incidence and nature of symptoms (solicited and unsolicited) reported during the 7-day (Days 0-6) post-vaccination period (Exposed set)	%LOGGEN
Template 17	Daily prevalence of any fever during the 7-day (Days 0-6) post-vaccination period (Exposed set)	%SYMPLLOT
Template 18	Incidence of solicited local symptoms reported during the 7-day (Days 0-6) post-vaccination period (Exposed set)	%FREQ
Template 19	Incidence of solicited local symptoms reported during the 7-day (Days 0-6) post-vaccination period by maximum intensity (Exposed set)	%FREQ
Template 20	Incidence of solicited general symptoms reported during the 7-day (Days 0-6) post-vaccination period (Exposed set)	%FREQ
Template 21	Incidence of solicited general symptoms reported during the 7-day (Days 0-6) post-vaccination period by maximum intensity (Exposed set)	%FREQ
Template 22	Percentage of subjects reporting the occurrence of unsolicited symptoms classified by MedDRA Primary System Organ Class	%UNSOL

	and Preferred Term, during the 30-day (Days 0-29) post-vaccination period (Exposed set)	
Template 23	Percentage of subjects reporting the occurrence of unsolicited symptoms classified by MedDRA Primary System Organ Class and Preferred Term, during the 30-day (Days 0-29) post-vaccination period (Exposed set)	%UNSOL
Template 24	Listing of SAEs reported up to study end (Exposed set)	%SAE
Template 25	Number (%) of subjects with serious adverse events up Day 7 (Exposed set)	%CTR_SAE
Template 26	Compliance in returning symptom information (Exposed set)	% COMPLI
Template 27	Number and percentage of subjects taking a concomitant medication during the 7- day (Days 0-6) post -vaccination period (Exposed set)	%CMED_INC
Template 28	Exploratory comparisons between groups in terms of percentage of subjects reported any Grade 2/3 AE and/or any fever >38.5°C and/or any vaccine-related SAE during the 7 day (Days 0-6) Post- vaccination period (Exposed set)	%COMP_FQ_AE
Template 29	Solicited and unsolicited symptoms experienced by at least 5 % of subjects , classified by MedDRA Primary System Organ Class and Preferred Term within the 30-day (Days 0-29) post-vaccination period including number of events - SAE excluded (Exposed set)	%UNSOL (NIH=5, EVENT=1)
Template 30	Distribution of change from baseline in haematology and biochemistry with respect to normal laboratory ranges (Exposed set)	%HAEMATO_BIOCH
Template 31	Summary of haematology and biochemistry results by maximum grade from VISIT 2 (D7) up to VISIT 3 (D30) versus baseline (Exposed set)	%HAEMATO_BIOCH_GR_CHANGE
Template 32	Summary of haematology and biochemistry results by maximum grade in the specified category from VISIT 2 (D7) up to VISIT 3 (D30) versus baseline (Exposed set)	%freq_dis
Template 33	Summary of haematology change from baseline by maximum grade from VISIT2 (D7) up to VISIT 3 (D30) (Exposed set)	%HAEMATO_BIOCH_GR_CHANGE
Template 34	Summary of haematology change from baseline by maximum grade in the specified category from VISIT2 (D7) up to VISIT3 (D30) (Exposed set)	%freq_dis
Template 35	Individual results of hemoglobin levels outside of the normal ranges in <group> (Exposed set)	%HB_PROFIL
Template 36	Number and percentage of subjects with anti-RSV-A neutralising antibody titer equal to or above <cut-off> and GMTs (Per protocol set)	%GMT
Template 37	Number and percentage of subjects with anti-RSV-A neutralising antibody titer equal to or above <cut-off> and GMTs - by age category (Per protocol set)	%GMT
Template 38	Geometric mean of the individual ratio of anti-RSV-A neutralising antibody titers at each post-vaccination timepoint compared to pre-vaccination with 95% CI (Per protocol set)	%GMRACT
Template 39	GMTs and their 95% CIs for anti-RSV-A neutralising antibody at each timepoint (Per protocol set)	%GMTPLOT*
Template 40	Kinetics of GMTs for anti-RSV-A neutralising antibody on subjects with results available at all timepoints (Per protocol set)	%KIN_GM*
Template 41	Distribution of anti-neogenin antibody concentration (Exposed set)	%DIS
Template 42	Distribution of fold of anti-neogenin antibody concentration (Exposed set)	%DIS
Template 43	Distribution of anti-RSV-A neutralising antibody titer (Per	%DIS

CONFIDENTIAL

204812 (RSV F-021)

Statistical Analysis Plan Amendment 4 Final

	protocol set)	
Template 45	Distribution of fold of anti-RSV-A neutralising antibody titer by cumulative pre-vaccination titer category (Per protocol set)	%DIS
Template 46	Reverse cumulative distribution curves for anti-RSV-A neutralising antibody titers in each group at pre-vaccination (Per protocol set)	%REVCUM
Template 47	Individual results of anti-RSV-A neutralising antibody titer at Day <30/60/90> versus pre-vaccination in <each group> and Control (Per protocol set)	%SCATTERPLOT*
Template 48	Vaccine response for anti-RSV-A neutralising antibody titer at each post-vaccination timepoint (Per protocol set)	%HUM_RESP*
Template 49	Estimated GMTs and 95% CIs for anti-RSV-A neutralising antibody titre (Per protocol set)	%GMT_ANOVA
Template 50	Exploratory comparisons (GMT ratios) between RSV groups with corresponding 95% confidence interval for anti-RSV A neutralizing antibody titre at Day 30 (Per protocol set)	%GMT_RATIO
Template 51	Individual kinetics of anti-neogenin antibody concentrations by group (Exposed set)	%NEO_INDKIN*
Template 52	GM of individual ratios (fold increase post over pre) and their 95% CIs for anti-RSV F IgG1 and IgG total antibody assays and each group, at Day 30 (Per protocol set)	%GMRPLOT*
Template 53	Exploratory comparisons (GM ratios of fold increase post/pre) between RSV groups with corresponding 95% confidence interval for anti-RSV F IgG1 antibody concentrations at Day 30 (Per protocol set)	%GMF_RATIO*
Template 54	Comparisons of GM ratios with corresponding 95% confidence interval between anti-RSV F antibody concentrations (IgG Total) and anti-RSV-A neutralising antibody titers at pre-vaccination (Per protocol set)	%GM_RATIO_PRE.SAS**
Template 55	Exploratory comparisons (GM ratios of fold increase post/pre) with corresponding 95% confidence interval between anti-RSV F antibody concentrations (IgG Total) and anti-RSV-A neutralising antibody titers at Day 30 (Per protocol set)	%GM_RATIO_FI.SAS**
Template 56	Desirability index of immunogenicity during the 30-day (Days 0-29) post-vaccination period (Per protocol set)	%Immuno_DI**
Template 57	Desirability index of reactogenicity during the 7-day (Days 0-6) post-vaccination period (Exposed set)	%Reacto_DI**
Template 58	Desirability index based on reactogenicity and safety (Exposed set up to Day 7) and immunogenicity (Per protocol set up to Day 30)	%Overall_DI**
Template 59	Percentage of subjects reporting solicited local symptoms (any grade / grade 3) during the 7-day post-vaccination period (Exposed set)	%GFREQ

* Name of specific macros created in study RSV F-001 (116969), RSV F-020 (201510)

** **Name of specific macros created in study RSV F-021 (204812)**

*** **It is the simplified version of Template 22 without UL and LL added for the final analysis**

Template 1 Number of subjects enrolled into the study as well as the number of subjects excluded from the PPS analyses with reasons for exclusion

Title	Total			<each group>	
	n	s	%	n	s
Total enrolled cohort					
Study vaccine dose not administered at all but subject number allocated (code 1030)					
Exposed set					
<Reason for elimination & elimination code>					
<Reason for elimination & elimination code>					
Per protocol set for immunogenicity					

<each group>:

30 PreF = 30 µg PreF

60 PreF = 60 µg PreF

120 PreF = 120 µg PreF

Control = Placebo

Note: Subjects may have more than one elimination code assigned

n = number of subjects with the elimination code assigned excluding subjects who have been assigned a lower elimination code number

s = number of subjects with the elimination code assigned

% = percentage of subjects in the considered Per protocol set relative to the Exposed set

Template 2 Number of subjects vaccinated, completed and withdrawn with reason for withdrawal (Exposed set)

	<each group>	Total
Number of subjects vaccinated		
Number of subjects completed		
Number of subjects withdrawn		
Reasons for withdraw:		
Serious Adverse Event		
Non-serious adverse event		
Protocol violation		
Consent withdrawal (not due to an adverse event)		
Migrated/moved from study area		
Lost to follow-up (subjects with incomplete vaccination course)		
Lost to follow-up (subjects with complete vaccination course)		
Others		

<each group>:

30 PreF = 30 µg PreF

60 PreF = 60 µg PreF

120 PreF = 120 µg PreF

Control = Placebo

Vaccinated = number of subjects who were vaccinated in the study

Completed = number of subjects who completed last study visit

withdrawn = number of subjects who did not come for the last study visit

Template 3 Number of subjects vaccinated, completed and withdrawn with reason for withdrawal (Exposed set)

	<each group>	Total
Number of subjects vaccinated		
Number of subjects completed		
Number of subjects withdrawn		
Reasons for withdrawal :		
Serious Adverse Event		
Non-Serious Adverse Event		
Protocol violation		
Consent withdrawal (not due to an adverse event)		
Migrated/moved from study area		
Lost to follow-up (subjects with incomplete vaccination course)		
Lost to follow-up (subjects with complete vaccination course)		
Sponsor study termination		
Other - <reason>		
Other - <reason>		

<each group>:

30 PreF = 30 µg PreF

60 PreF = 60 µg PreF

120 PreF = 120 µg PreF

Control = Placebo

Vaccinated = number of subjects who were vaccinated in the study

Completed = number of subjects who completed last study visit

Withdrawn = number of subjects who did not come for the last study visit

Template 4 Number of subjects at each visit and list of withdrawn subjects (Exposed set)

Group	Visit	N	Withdrawn Subject number	Reason for withdrawal
<each group>	VISIT 1 (D0)			
	VISIT 2 (D7)			
	VISIT 3 (D30)			
	VISIT 4 (D60)			
	VISIT 5 (D90)			

<each group>:

30 PreF = 30 µg PreF

60 PreF = 60 µg PreF

120 PreF = 120 µg PreF

Control = Placebo

N = Number of subjects who are still in the study up to the visit

Withdrawn = Subject who did not return after the visit

Template 5 Summary of demographic characteristics (Per Protocol Set)

		<each group> (N=)		Total (N=)	
Characteristics	Parameters or Categories	Value or n	%	Value or n	%
Age (years) at vaccination	Mean				
	SD				
	Median				
	Minimum				
	Maximum				
Ethnicity	American Hispanic or Latino				
	Not American Hispanic or Latino				
Geographic Ancestry	African Heritage / African American				
	American Indian or Alaskan Native				
	Asian - Central/South Asian Heritage				
	Asian - East Asian Heritage				
	Asian - Japanese Heritage				
	Asian - South East Asian Heritage				
	Native Hawaiian or Other Pacific Islander				
	White - Arabic / North African Heritage				
	White - Caucasian / European Heritage				
	Other				

<each group>:

30 PreF = 30 µg PreF

60 PreF = 60 µg PreF

120 PreF = 120 µg PreF

Control = Placebo

N = total number of subjects

n/% = number / percentage of subjects in a given category

Value = value of the considered parameter

SD = standard deviation

Template 6 Summary of demographic characteristics by age category (Exposed set)

		<each group> (N=)				Total (N=)			
		<subgroup>		<subgroup>		<subgroup>		<subgroup>	
Characteristics	Parameters or Categories	Value or n	%	Value or n	%	Value or n	%	Value or n	%
Age (years) at vaccination	Mean								
	SD								
	Median								
	Minimum								
	Maximum								
Ethnicity	American Hispanic or Latino								
	Not American Hispanic or Latino								
Geographic Ancestry	African Heritage / African American								
	American Indian or Alaskan Native								
	Asian - Central/South Asian Heritage								
	Asian - East Asian Heritage								
	Asian - Japanese Heritage								
	Asian - South East Asian Heritage								
	Native Hawaiian or Other Pacific Islander								
	White - Arabic / North African Heritage								
	White - Caucasian / European Heritage								
Other									

<each group>:

30 PreF = 30 µg PreF

60 PreF = 60 µg PreF

120 PreF = 120 µg PreF

Control = Placebo

N = total number of subjects

n/% = number / percentage of subjects in a given category

Value = value of the considered parameter

SD = standard deviation

<subgroup> by age category:

18-32Y = 18-32 years old subjects

33-45Y = 33-45 years old subjects

Template 7 Number of subjects by center (Exposed set)

	<each group>		Total	
Center	n		n	%
PPD				
PPD				
..				
All				

<each group>:

30 PreF = 30 µg PreF
 60 PreF = 60 µg PreF
 120 PreF = 120 µg PreF
 Control = Placebo
 n = number of subjects included in each group or in total for a given center or for all centers
 All = sum of all subjects in each group or in total (sum of all groups)
 % = n/All x 100
 Center = GSK Biologicals assigned center number

Template 8 Number of subjects by center for each age category (Exposed set)

	30 PreF		60 PreF		120 PreF		Control		Total			
	18-32Y	33-45Y	18-32Y	33-45Y	18-32Y	33-45Y	18-32Y	33-45Y	18-32Y		33-45Y	
Center	n	n	n	n	n	n	n	n	n	%	n	%

30 PreF = 30 µg PreF
 60 PreF = 60 µg PreF
 120 PreF = 120 µg PreF
 Control = Placebo
 18-32Y = 18-32 years old subjects
 33-45Y = 33-45 years old subjects
 n = number of subjects included in each group or in total for a given center or for all centers
 All = sum of all subjects in each group or in total (sum of all groups)
 % = n/All x 100
 Center = GSK Biologicals assigned center number

Template 9 Number of subjects by country and center (Exposed set)

		<each group>		Total	
Country	Center	n		n	%
	...				
	All				
	...				
All	All				

<each group>:

30 PreF = 30 µg PreF
 60 PreF = 60 µg PreF
 120 PreF = 120 µg PreF
 Control = Placebo
 n = number of subjects included in each group or in total for a given center or for all centers
 All = sum of all subjects in each group or in total (sum of all groups)
 % = n/All x 100
 Center = GSK Biologicals assigned center number

Template 10 Deviations from specifications for age and intervals between study visits (Exposed set)

		Age	Dose:1-PI (D30)	Dose:1-PI (D60)	Dose:1-PI (D90)	Dose:1-CONCLUSION
Group		Protocol	Protocol	Protocol	Protocol	Protocol
		from 18 to 45 years	from 30 to 44 days	from 56 to 70 days	from 86 to 100 days	from 330 to 390 days
<each group>	n					
	N					
	%					
	range					

<each group>:

30 PreF = 30 µg PreF

60 PreF = 60 µg PreF

120 PreF = 120 µg PreF

Control = Placebo

N = total number of subjects with available results

n/% = number / percentage of subjects with results outside of the interval

range = minimum-maximum for age and intervals

PI(D30) = Post-vaccination at Day 30

PI(D60) = Post-vaccination at Day 60

PI(D90) = Post-vaccination at Day 90

Template 11 Summary of vital signs characteristics at VISIT 1 (Day 0) (Exposed set)

		<each group> N =	Total N =
Characteristics	Parameters	Value	Value
Height (Cm)	Mean		
	SD		
	Median		
	Minimum		
	Maximum		
	Unknown		
Weight (Kg)	Mean		
	SD		
	Median		
	Minimum		
	Maximum		
	Unknown		
Heart rate (Beats per minute)	Mean		
	SD		
	Median		
	Minimum		
	Maximum		
	Unknown		
Respiratory rate (Breadth per minute)	Mean		
	SD		
	Median		
	Minimum		
	Maximum		
	Unknown		
Systolic blood pressure (MmHg)	Mean		
	SD		
	Median		
	Minimum		
	Maximum		
	Unknown		
Diastolic blood pressure (MmHg)	Mean		
	SD		
	Median		
	Minimum		
	Maximum		
	Unknown		

<each group>:

30 PreF = 30 µg PreF

60 PreF = 60 µg PreF

120 PreF = 120 µg PreF

Control = Placebo

N = total number of subjects

Value = value of the considered parameter

SD = standard deviation

Template 12 Study Population (Exposed set)

Number of subjects	<each group>	Total
Planned, N		
Randomised, N (Exposed set)		
Completed, n (%)		
Demographics	<each group>	Total
N (Exposed set)		
Females:Males		
Mean Age, years (SD)		
Median Age, years (minimum, maximum)		
White - caucasian / european heritage, n (%)		
Asian – South East Asian heritage, n (%)		

<each group>:

30 PreF = 30 µg PreF

60 PreF = 60 µg PreF

120 PreF = 120 µg PreF

Control = Placebo

Template 13 Number of enrolled subjects by country

		<each group> N =	Total N =
Characteristics	Categories	n	n
Country	Czech Republic		
	Australia		
	...		

<each group>:

30 PreF = 30 µg PreF

60 PreF = 60 µg PreF

120 PreF = 120 µg PreF

Control = Placebo

N = Number of enrolled subjects

n= number of enrolled subjects included in each group or in total for a given country or for all countries

Template 14 Number of enrolled subjects by age category

		<each group> N =	Total N =
Characteristics	Categories	n	n
Age category	Adults (18-45 years)		
	Missing		

<each group>:

30 PreF = 30 µg PreF

60 PreF = 60 µg PreF

120 PreF = 120 µg PreF

Control = Placebo

N = Number of enrolled subjects

n= number of enrolled subjects included in each group or in total for a given age category or for all age categories

Missing = age at dose 1 unknown

Template 15 Minimum and maximum activity dates (Exposed set)

Group	Activity number	Activity Description	Minimum date	Maximum date
<each group>	10	VISIT 1 (DAY 0)		
	20	VISIT 2 (M 1)		
	30	VISIT 3 (M 2)		
	40	VISIT 4 (M 3)		

<each group>:

30 PreF = 30 µg PreF

60 PreF = 60 µg PreF

120 PreF = 120 µg PreF

Control = Placebo

Template 16 Incidence and nature of symptoms (solicited and unsolicited reported during the 7-day (Days 0-6) post-vaccination period (Exposed set)

Group	Any symptom					General symptoms					Local symptoms				
	N	n	%	95% CI		N	n	%	95% CI		N	n	%	95% CI	
				LL	UL				LL	UL				LL	UL
<each group>															

<each group>:

30 PreF = 30 µg PreF

60 PreF = 60 µg PreF

120 PreF = 120 µg PreF

Control = Placebo

[figure not shown]
N = number of subjects with the administered dose

n/% = number/percentage of subjects presenting at least one type of symptom whatever the study vaccine administered

95% CI = exact 95% confidence interval, LL = Lower Limit, UL = Upper Limit

Note: the same table will be generated by group/sub-group, with sub-group= age category (see SAP).

Template 17 Daily prevalence of any fever during the 7-day (Days 0-6) post-vaccination period (Exposed set)

30 PreF = 30 µg PreF

60 PreF = 60 µg PreF

120 PreF = 120 µg PreF

Control = Placebo

Template 18 Incidence of solicited local symptoms reported during the 7-day (Days 0-6) post-vaccination period (Exposed set)

		<each group>				
					95 % CI	
Symptom	Type	N	n	%	LL	UL
Pain	All					
	Grade 1					
	Grade 2					
	Grade 3					
	Onset ≤48h					
	Medical advice					
Redness (mm)	All					
	>20 and ≤ 50					
	>50 and ≤ 100					
	>100					
	Onset ≤48h					
	Medical advice					
Swelling (mm)	All					
	>20 and ≤ 50					
	>50 and ≤ 100					
	>100					
	Onset ≤48h					
	Medical advice					

